MTX Methotrexate

NSAIDs Nonsteroidal anti-inflammatory drugs OC/RDC Oracle Clinical/Remote Data Capture

o.d. once a day

PFS Pre-filled syringe

p.o. per orally

SAE serious adverse event

s.c. subcutaneous

SpA Spondyloarthritides

SUSAR Suspected Unexpected Serious Adverse Reactions

TNFα tumor necrosis factor alpha,

VAS visual analog scale

WHO World Health Organization

Glossary of terms

Assessment	A procedure used to generate data required by the study
Dose level	The dose of drug given to the patient (total daily or weekly etc.)
Enrollment	Point/time of patient entry into the study at which informed consent must be obtained (i.e. prior to starting any of the procedures described in the protocol)
Investigational treatment	All investigational drug(s) whose properties are being tested in the study as well as their associated treatment controls. This includes any placebos, any active controls, as well as approved drugs used outside of their indication/approved dosage or tested in a fixed combination. Investigational treatment generally does not include protocolspecified concomitant background therapies when these are
	standard treatments in that indication
Medication number	A unique identifier on the label of each investigational/study drug package in studies
Period	A subdivision of a cross-over study
Premature subject/patient withdrawal	Point/time when the patient exits from the study prior to the planned completion of all study treatment administration and/or assessments; at this time all study treatment administration is discontinued and no further assessments are planned, unless the patient will be followed for progression and/or survival
Randomization number	A unique identifier assigned to each randomized patient, corresponding to a specific treatment arm assignment
Study drug/ treatment	Any single drug or combination of drugs administered to the patient as part of the required study procedures; includes investigational drug (s), active drug run-ins or background therapy
Study/investigational treatment discontinuation	Point/time when patient permanently stops taking study/investigational treatment for any reason; may or may not also be the point/time of premature patient withdrawal
Subject Number	A number assigned to each patient who enrolls into the study
Variable	A measured value or assessed response that is determined in specific assessments and used in data analysis to evaluate the drug being tested in the study

Amendment 1

Amendment rationale

This protocol amendment is issued for the following reasons:

- Based on results from MEASURE III (CAIN457F2314), MEASURE IV (CAIN457F2320) and COAST V (Ixekizumab NCT02696785) studies, the assumptions for the power calculation of the primary and a selection of secondary and exploratory objectives were reevaluated, leading to changes in the statistical analysis plan. The three studies mentioned above suggest that the placebo response might be somewhat higher, leading to a potentially smaller difference between active treatment and placebo than assumed during the planning of this trial. Therefore, in order to keep sufficient power, it was decided to pool the two Secukinumab arms for the primary analysis. This new evaluation triggered an adaption of a set of objectives. The primary objective was adapted so that data of *Group 1* (Secukinumab 150 mg s.c. "delayed tapering") and of *Group 2* (Secukinumab 150 mg s.c. "early tapering") are pooled and ASAS20 response at week 12 are compared against placebo. For the other reevaluated secondary and exploratory objectives, data is pooled and is compared against placebo according to the same schema. In the course of this amendment the amount of randomized patients can be reduced to a smaller size (approx. 190) than originally expected (approx. 204), while maintaining adequate power for primary and secondary analyses.
- The amendment is used to describe the ASAS Health Index (chapter 6.4.9) in a more detailed way. Besides the 17 aspects of health, the 9 questions regarding environmental factors in patients with AS are mentioned.

None of the changes described in this amended protocol are made due to newly emerged safety considerations.

1 Introduction

1.1 Background

Ankylosing spondylitis (AS) is a chronic inflammatory disease which belongs to a group of conditions known as spondyloarthritides (SpA). It is mainly characterized by involvement of the axial skeleton and sacroiliac joints, but also affects peripheral joints, entheses and extra-articular organs. A significant proportion of patients may present with associated extra-articular manifestations such as uveitis, psoriasis, inflammatory bowel disease, cardiovascular and pulmonary abnormalities. IL-17A has been shown to play an important role in driving the body's immune response in psoriasis and SpA conditions, including PsA and AS (Van Baarsen et al 2011).

Cosentyx® (Secukinumab) is a recombinant monoclonal antibody that neutralizes the activity of IL-17A. Secukinumab is the first IL-17A inhibitor with positive Phase 3 results for the treatment of PsA and AS. In January 2015, Secukinumab (at a dose of 300 mg) became the first IL-17A inhibitor approved in Europe as a first-line systemic treatment for moderate-to-severe plaque psoriasis in adult patients, and in the United States (US) as a treatment for moderate-to-severe plaque psoriasis in adult patients who are candidates for systemic therapy or phototherapy (light therapy). Secukinumab

Clinical trials of Secukinumab in ankylosing spondylitis

The safety and efficacy of Secukinumab has been assessed in 590 patients in 2 randomized, double-blind, placebo-controlled, Phase 3 studies (MEASURE 1: CAIN457F2305; and MEASURE 2: CAIN457F2310, Sieper et al 2015) in patients with active AS with a Bath Ankylosing Spondylitis Disease Activity Index (BASDAI) \geq 4 despite non-steroidal anti-inflammatory drugs (NSAIDs), corticosteroid or disease-modifying anti-rheumatic drug (DMARD) therapy. The efficacy and safety of Secukinumab 75 mg and 150 mg were evaluated vs. placebo with either an i.v. or s.c. loading regimen. In the MEASURE 1 and MEASURE 2 study, 27.0% and 38.8% of patients, respectively, were previously treated with an anti-TNF α agent and discontinued the anti-TNF α agent due to either lack of efficacy or intolerance (anti-TNF α -IR patients). The primary endpoint was at least a 20% improvement in Assessment of Spondyloarthritis International Society (ASAS20) criteria at Week 16.

In both AS studies, Secukinumab-treated patients (150 mg in MEASURE 2 and both regimens in MEASURE 1) demonstrated significantly improved signs and symptoms at Week 16; a comparable magnitude of response and efficacy was maintained up to Week 52. The magnitude of response (treatment difference versus placebo) with regards to signs and symptoms at Week 16 was similar in anti-TNF α -naïve and anti-TNF α -inadequate responder patients in both studies, with higher absolute response rates in anti-TNF α -naïve patients. Efficacy was maintained in anti-TNF α -naïve and anti-TNF α -IR patients up to Week 52 in both studies.

In MEASURE 2, treatment with Secukinumab 150 mg resulted in greater improvement in ASAS20, ASAS40, high-sensitivity C-reactive protein (hsCRP), ASAS 5/6 and BASDAI score compared with placebo at Week 16. The onset of action of Secukinumab 150 mg occurred as early as Week 1 for ASAS20 (superior to placebo). ASAS20 responses were improved at Week 16 in both anti-TNF α -naïve patients (68.2% vs. 31.1%; p<0.05) and anti-TNF α -IR patients (50.0% vs. 24.1%; p<0.05) for Secukinumab 150 mg compared with placebo, respectively.

Non-steroidal anti-inflammatory drugs in ankylosing spondylitis

NSAIDs (including COX-1 or COX-2 inhibitors) are the standard therapy for patients with AS (van der Hejde et al 2011). While effective in relieving pain and improving disease activity in many patients, NSAIDs are associated with side effects that may cause concerns particularly in the context of a life-long treatment at high daily intake doses for diseases such as AS. For example, it has recently been shown that the NSAID diclofenac increases the risk of myocardial infarction in patients with SpA (Dubreuil et al 2014). NSAIDs have also been associated with gastrointestinal side effects (Lanas et al 2006) and a potential acceleration of chronic kidney disease progression (Nderitu et al 2013).

According to the ASAS / European League Against Rheumatism (EULAR) recommendations (van der Hejde et al 2011), patients who show an inadequate response to at least 2 NSAIDs administered at the maximum recommended dose over a total period of 4 weeks should be treated with a biologic. When switching to a biologic in clinical practice, the refractory NSAID treatment is often kept as a concomitant treatment to the biologic. There is currently no clinical or scientific guidance on how, when and how fast NSAIDs should be discontinued or tapered after initiation of the biologic treatment.

Clinical trials have already shown that NSAID intake could be considerably reduced in AS patients treated with anti- TNF compounds (e.g. Poddubnyy et al 2013, Konttinen et al 2007, Braun et al 2002). In these studies, NSAID usage could be reduced in over 50% of patients by more than 50% of the baseline value and could even be completely stopped in up to 20% of the analyzed patients (Braun et al 2002). However, in these trials, patients were not explicitly advised how to reduce NSAIDs. Furthermore, the nonsteroidal anti-inflammatory drug assessment of the spondyloarthritis international society score (ASAS-NSAID score), which has been developed as a standardized method of evaluating NSAID intake in clinical trials has not been used as an endpoint in many of the trials (Dougados et al 2011).

In a recently published prospective, randomized, placebo-controlled trial on the NSAID sparing effect of etanercept (Dougados et al 2014), a dramatic reduction of NSAID intake (up to two thirds) was observed. However, the reduction in NSAID intake was associated with considerably lower clinical ASAS20 response rates compared to the Phase 3 clinical trial of etanercept in AS (i.e. 44% vs. 57% at Week 8). This finding raises questions as to whether or not reducing NSAIDs may potentially counteract the achievement of treatment goals (i.e. reduction of disease activity) and whether or not there is an optimal time point for starting NSAID tapering.

1.2 Purpose

The current study will assess the clinical ASAS20 response to Secukinumab and evaluate to which extent concomitant NSAID treatment can be reduced between Week 4 and Week 12 in patients treated with Secukinumab 150 mg or placebo. Furthermore, the clinical trial will assess the clinical ASAS20 response to Secukinumab and evaluate to which extent concomitant NSAID treatment can be reduced between Week 4 and Week 12 in patients treated with Secukinumab 150 mg or placebo following an initial run-in phase of 4 weeks on stable NSAID therapy. Two different time points of NSAID tapering initiation will be evaluated in this study:

1. a delayed tapering approach in which NSAID will be tapered following 4 weeks of Secukinumab treatment at stable NSAID therapy.

2. an early tapering approach in which NSAID will be tapered immediately after initiation of Secukinumab treatment

These 2 approaches will be evaluated compared to placebo in order to assess whether the early or delayed NSAID tapering is superior to placebo in terms of clinical ASAS20 response and extent of reduction in NSAID intake.

As a patient-reported outcome, pain is a major patient-relevant efficacy parameter in clinical practice in AS. This study will therefore monitor overall neck, back and hip pain on a continuous basis. It will be recommended that NSAID should be tapered if the patient reports an improvement in back pain or a level below a certain threshold. It is anticipated that the results of this study may provide guidance for the systematic adjustment of concomitant NSAID treatment in AS patients based on their initial response to Secukinumab, thereby leading to optimization of the therapeutic strategy with Secukinumab. In case of a positive outcome concerning the NSAID reduction, e.g. no drop in clinical efficacy for Secukinumab between Week 4 and Week 12 at significantly reduced NSAID intake, this study could trigger the development of a guidance concerning NSAID reduction applicable for all AS patients starting a biologic treatment.

2 Study objectives

2.1 **Primary objective**

To demonstrate that the efficacy of Secukinumab 150 mg s.c. (with NSAID tapering) is superior to placebo based on the proportion of patients achieving an ASAS20 response at week 12. To show superiority, both Secukinumab treatment arms will be pooled and compared against placebo.

2.2 Secondary objectives

- 1. To demonstrate that the change from baseline in ASAS-NSAID score at week 12 is superior for Secukinumab 150 mg s.c. as compared to placebo. To show superiority, both Secukinumab treatment arms will be pooled and compared against placebo.
- 2. To demonstrate that the efficacy of Secukinumab 150 mg s.c at week 12 is superior to placebo based on the change from baseline in the total BASDAI. To show superiority, both Secukinumab treatment arms will be pooled and compared against placebo.
- 3. To demonstrate that the efficacy of Secukinumab 150 mg s.c. (Secukinumab from week 0 with NSAID tapering allowed from week 4; "delayed tapering") at Week 12 is superior to placebo based on the proportion of patients achieving an ASAS20 response.
- 4. To demonstrate that the efficacy of Secukinumab 150 mg s.c. (Secukinumab from week 4 with NSAID tapering allowed from week 4; "early tapering") at Week 12 is superior to placebo based on the proportion of patients achieving an ASAS20 response.
- 5. To demonstrate that the efficacy of Secukinumab 150 mg s.c. (Secukinumab from week 4 with NSAID tapering allowed from week 4; "early tapering") at Week 16 is superior to placebo based on the proportion of patients achieving an ASAS20 response.

- To demonstrate that the change from baseline in ASAS-NSAID score at Week 12 is superior for Secukinumab 150 mg s.c. (Secukinumab from week 0 with NSAID tapering allowed from week 4; "delayed tapering") as compared to placebo.
- 7. To demonstrate that the change from baseline in ASAS-NSAID score at Week 12 is superior for Secukinumab 150 mg s.c. (Secukinumab from week 4 with NSAID tapering allowed from week 4; "early tapering") as compared to placebo.
- 8. To demonstrate that the efficacy of Secukinumab 150 mg s.c. (Secukinumab from week 0 with NSAID tapering allowed from week 4; "delayed tapering") at Week 12 is superior to placebo based on the change from baseline in the total BASDAI.
- 9. To demonstrate that the efficacy of Secukinumab 150 mg s.c. (Secukinumab from week 4 with NSAID tapering allowed from week 4; "early tapering") at Week 12 is superior to placebo based on the change from baseline in the total BASDAI.
- 10. To demonstrate that the efficacy of Secukinumab 150 mg s.c. (Secukinumab from week 4 with NSAID tapering allowed from week 4; "early tapering") at Week 16 is superior to placebo based on the change from baseline in the total BASDAI.
- 11. To demonstrate that the efficacy of Secukinumab 150 mg s.c. at week 12 is superior to placebo based on the change from baseline in health-related Quality of Life as measured by the SF-36 PCS.
- 12. To demonstrate that the efficacy of Secukinumab 150 mg s.c. (Secukinumab from week 0 with NSAID tapering allowed from week 4; "delayed tapering") at Week 12 is superior to placebo based on the change from baseline in health-related Quality of Life as measured by the SF-36 PCS.
- 13. To demonstrate that the efficacy of Secukinumab 150 mg s.c. (Secukinumab from week 4 with NSAID tapering allowed from week 4; "early tapering") at Week 12 is superior to placebo based on the change from baseline in health-related Quality of Life as measured by the SF-36 PCS.
- 14. To compare between both Secukinumab regimens concerning the change from baseline in ASAS-NSAID score after 12 weeks of Secukinumab exposure (ASAS-NSAID index at Week 12 for "delayed tapering" vs. Week 16 for "early tapering").

2.3 **Exploratory objectives**

- 1. To compare between both Secukinumab regimens concerning the change from baseline in the BASDAI after 12 weeks of Secukinumab exposure (BASDAI at Week 12 for "delayed tapering" vs. Week 16 for "early tapering").
- 2. To evaluate change in patient reported neck, back and hip pain (BASDAI question 2; Appendix 4) beginning from Secukinumab treatment on a continuous basis in patients exposed to Secukinumab 150 mg s.c. for 12 weeks vs. placebo.
- 3. To evaluate change in patient reported neck, back and hip pain (BASDAI question 2; Appendix 4) from baseline on a continuous basis in patients randomized Secukinumab 150 mg s.c. (Secukinumab from week 0 with NSAID tapering allowed from week 4; "delayed tapering") vs. placebo from week 0 to week 12.
- 4. To evaluate change in patient reported neck, back and hip pain (BASDAI question 2; Appendix 4) from baseline on a continuous basis in patients randomized Secukinumab 150 mg s.c. (early tapering) vs. placebo from week 0 to week 16.

Amended Protocol Version v01 Clean

- To compare ASAS20 response rates at week 4 in Secukinumab 150 mg. s.c. (Secukinumab from week 0 with NSAID tapering allowed from week 4; "delayed tapering") vs. week 20 in the patients switching from Placebo after 4 weeks of Secukinumab exposure each.
- 6. Total ASAS-NSAID [Area Under Curve (AUC)] Score from treatment start with Secukinumab to a Secukinumab exposure of 12 weeks.
- 7. Total ASAS-NSAID [Area Under Curve (AUC)] Score from Week 4 to Week 16 for each treatment arm
- 8. Proportion of patients with no NSAID intake after Secukinumab exposure of 12 weeks
- 9. Proportion of patients with no NSAID intake at week 12
- 10. Change from Baseline in the ASAS Health Index after Secukinumab exposure of 12 weeks
- 11. Change from Baseline in the ASAS Health Index at week 12
- 12. Spinal mobility assessed by Bath Ankylosing Spondylitis Metrology Index (BASMI) linear scores
- 13. ASAS40 response rate over time
- 14. ASAS20 response rate over time
- 15. ASAS5/6 response rate over time
- 16. Change from baseline in hsCRP
- 17. Change from baseline in total BASDAI over time
- 18. BASDAI 50 response over time
- 19. ASAS partial remission over time
- 20. Change from baseline in ASAS components, including:
 - a. Patient's global assessment of disease activity
 - b. Total spinal pain
 - c. Inflammation as measured by the mean of BASDAI questions 5 and 6
 - d. Bath Ankylosing Spondylitis Functional Index (BASFI)
- 21. Change from baseline in Ankylosing Spondylitis Disease Activity Score (ASDAS)-C-Reactive Protein (CRP) and ASDAS-Erythrocyte Sedimentation Rate (ESR)
- 22. ASDAS inactive disease as defined by ASDAS < 1.3
- 23. ASDAS clinically important improvement (change in ASDAS \geq 1.1) and major improvement (change in ASDAS ≥ 2.0)
- 24. To assess overall tolerability and safety of Secukinumab at reduced NSAID intake.
- 25. To evaluate the reasons given by the patient in the patient diary on why he was not able to taper NSAIDs despite reduced spinal pain
- 26. To compare both Secukinumab regimens between week 12 (delayed tapering) and week 16 (early tapering) concerning all primary, secondary and exploratory objectives [at these timepoints, patients will have had the same exposure time to Secukinumab of 12 weeks]

3 Investigational plan

[figure not shown]

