3.1 Study design

This is a 20-week, randomized, double-blind, 3-arm, placebo-controlled, parallel-group, multicenter study of Secukinumab (AIN457) to examine the clinical response as measured by the ASAS20 and the NSAID-sparing effect of Secukinumab treatment. The clinical efficacy (ASAS20 response) and the cumulative NSAID sparing effect of two strategies of NSAID tapering after initiation of Secukinumab will be evaluated as compared to placebo:

Patients will be randomized 1:1:1 to one of the following treatment groups:

- Secukinumab delayed NSAID tapering: Secukinumab 150 mg s.c. at weeks 0, 1, 2, 3, 4, 8, 12, 16 and 20 with placebo injections at Week 5, 6, 7 and 17, 18, 19 to maintain the blind.
- **Secukinumab early NSAID tapering:** Placebo at weeks 0, 1, 2, 3 to maintain the blind; followed by Secukinumab 150 mg s.c. at Week 4, 5, 6, 7, 8, 12, 16 and 20 with intermittent Placebo injections at week 17, 18, 19 to maintain the blind.
- **Placebo:** Placebo at weeks 0, 1, 2, 3, 4, 5, 6, 7, 8 and 12. After the Week 16 assessments of the secondary endpoint have been performed, these patients will receive Secukinumab 150 mg s.c. at weeks 16, 17, 18, 19 and 20.

The patients will be stratified at randomization according to their status of prior TNF α inhibitor exposure, i.e. TNF α inhibitor naive patients or TNF α inhibitor inadequate responders (TNF α -IR). The only condition that will be placed on enrollment targets for each stratum is that no less than 60% of patients (122 patients) are TNF α inhibitor naïve, i.e., no more than 40% of patients (82 patients) are TNF α -IR. In theory the percentage of TNF α inhibitor naïve patients could reach 100%, although that is not anticipated.

All patients will be advised to continue on the maximum recommended/tolerated dose of NSAIDs for the first 4 weeks of the trial.

A follow-up visit is to be done 4 weeks after last study treatment administration for all subjects, regardless of whether they complete the entire study as planned or discontinue prematurely.

NSAID tapering strategy

All patients will be advised to taper/discontinue their NSAID intake starting at Week 4 to Week 20. Patients may use NSAIDs on an on-demand basis to avoid an unacceptable worsening of disease activity.

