9.5 Analysis of other variables

9.5.1 Secondary efficacy variables

The secondary efficacy variables are listed below. Secondary efficacy variables will be analyzed using the FAS population.

- ASAS20 response at Week 12/16.
- ASAS-NSAID response at Week 12.
- Change from baseline in BASDAI at Week 12/16.
- Change from baseline in SF36 physical component score at Week 12/16.
- Change from baseline in ASAS-NSAID score at Week 12 for Secukinumab (delayed tapering) vs. change from baseline in ASAS-NSAID score at Week 16 for Secukinumab (early tapering)
- Change from baseline in BASDAI at Week 12 for Secukinumab (delayed tapering) vs change from baseline in BASDAI at Week 16 for Secukinumab (early tapering).
- Change from baseline in BASDAI question 2
- ASAS20 response at Week 4 for Secukinumab (delayed tapering) vs. ASAS20 response at Week 20 for placebo group

Testing strategy

The following hypotheses will be included in the testing strategy, and type-I-errors will be set such that a family-wise type-I-error of 5% is kept:

Primary objective:

H₁: Secukinumab 150 mg s.c. (pooled Secukinumab groups) is not different to placebo regimen with respect to signs and symptoms (ASAS20 response) at Week 12

Secondary objectives:

H₂: Secukinumab 150 mg s.c. (pooled Secukinumab groups) is not different to placebo regimen with respect to change from baseline in ASAS-NSAID score at Week 12

H₃: Secukinumab 150 mg s.c. (pooled Secukinumab groups) is not different to placebo regimen with respect to change from baseline in total BASDAI score at Week 12

H₄: Secukinumab 150 mg s.c. (delayed tapering) is not different to placebo regimen with respect to signs and symptoms (ASAS20 response) at Week 12

H₅: Secukinumab 150 mg s.c. (early tapering) is not different to placebo regimen with respect to signs and symptoms (ASAS20 response) at Week 12

H₆: Secukinumab 150 mg s.c. (early tapering) is not different to placebo regimen with respect to signs and symptoms (ASAS20 response) at Week 16

H₇: Secukinumab 150 mg s.c. (delayed tapering) is not different to placebo regimen with respect to change from baseline in ASAS-NSAID score at Week 12

[figure not shown]
H₈: Secukinumab 150 mg s.c. (early tapering) is not different to placebo regimen with respect to change from baseline in ASAS-NSAID score at Week 12

H₉: Secukinumab 150 mg s.c. (delayed tapering) is not different to placebo regimen with respect to change from baseline in total BASDAI score at Week 12

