9.7 Sample size calculation

All sample size and power considerations are performed using EAST 6.

The sample size was calculated based on the phase III results of the MEASURE2 study, which used the same dose and loading regimen as will be applied in this trial. Under the assumption of 56.9% ASAS20 responders in the Secukinumab (delayed tapering) group and 27.0% in the placebo group, a sample size of 62 patients per group is required to have 90% power to show superiority of Secukinumab over placebo at a two sided $\alpha=5\%$.

For the comparison of the the early tapering group at week 16 vs. placebo, the same treatment effect is expected, leading to the same sample size. To compensate for some dropout and other protocol deviations, the sample size will be increased to 68 per arm. The total sample size of this trial will thus be 204. At the time of writing this amendment, about 190 patients have been recruited into this trial and it seems unlikely that a sample > 200 can be recruited within reasonable time. With this sample size, the (newly introduced) comparison of pooled

Secukinumab groups vs. placebo, the trial would still have almost 80 % (78%) power if the placebo response was somewhat higher (35%) than originally assumed...

Other secondary endpoints

It will be assumed that the amount of NSAID reduction observed in the etanercept SPARSE trial (Dougados et al. 2014), of 63.9 vs. baseline (etanercept) and 36.6 for placebo, with an estimated standard deviation of 40 will be seen in this trial for both Secukinumab groups versus placebo. Based on this assumption both secukinmab groups will have >90% power to show superiority over placebo for NSAID reduction.

For the total BASDAI parameter, 62 patients per treatment group should yield a power of approximately 91%, assuming a a treatment difference of 1.8 with a standard deviation of 2.8 (van der Heijde 2006). For SF-36 PCS, 62 patients per treatment group yield a power of approximately 87.5%, assuming mean change of 6.9 on both Secukinumab regimen and mean change of 1.6 on placebo with common standard deviation of 8.7 (Davis 2007).

10 Ethical considerations

Study documentation, record keeping and retention of documents

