## 2 Statistical methods

### 2.1 Data analysis general information

The data will be analyzed by Novartis on all patient data after database lock for the respective trial period. It is planned that the data from all centers that participate in this protocol will be used for analysis. Analysis datasets and statistical outputs will be produced using the most recent SAS® Version 9.4 (SAS Institute Inc., Cary, NC, USA), and stored in Novartis global programming & statistical environment (GPS).

Continuous data will be summarized by n, mean, standard deviation (SD), median, first and third quartiles, minimum and maximum. Categorical data will be presented by absolute and relative frequencies (n and %). Summary statistics will also be presented graphically wherever applicable.

If not otherwise specified, p-values and confidence intervals will be two-sided. Unless otherwise stated, the level of significance will be set to 5% (two-sided, family-wise type-I-error).

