#### Secondary objectives:

- H2: Secukinumab 150 mg s.c. (pooled Secukinumab groups) is not different to placebo regimen with respect to change from baseline in ASAS-NSAID score at Week 12
- H3: Secukinumab 150 mg s.c. (pooled Secukinumab groups) is not different to placebo regimen with respect to change from baseline in total BASDAI score at Week 12
- H4: Secukinumab 150 mg s.c. (delayed tapering) is not different to placebo regimen with respect to signs and symptoms (ASAS20 response) at Week 12
- H5: Secukinumab 150 mg s.c. (early tapering) is not different to placebo regimen with respect to signs and symptoms (ASAS20 response) at Week 12
- H6: Secukinumab 150 mg s.c. (early tapering) is not different to placebo regimen with respect to signs and symptoms (ASAS20 response) at Week 16.
- H7: Secukinumab 150 mg s.c. (delayed tapering) is not different to placebo regimen with respect to change from baseline in ASAS-NSAID score at Week 12.
- H8: Secukinumab 150 mg s.c. (early tapering) is not different to placebo regimen with respect to change from baseline in ASAS-NSAID score at Week 12.
- H9: Secukinumab 150 mg s.c. (delayed tapering) is not different to placebo regimen with respect to change from baseline in total BASDAI score at Week 12.
- H10: Secukinumab 150 mg s.c. (early tapering) is not different to placebo regimen with respect to change from baseline in total BASDAI score at Week 12
- H11: Secukinumab 150 mg s.c. (early tapering) is not different to placebo regimen with respect to change from baseline in total BASDAI score at Week 16.

These hypotheses will in principal be tested hierarchically in ascending order. However, since some hypotheses for individual group comparisons are already contained in the higher-ranked, pooled comparisons for the same endpoint (i.e. H4 and H5 are contained in H1, H7 and H8 are contained in H2 and H9 and H10 are contained in H3) these individual hypothesis can be tested simultaneously. The justification is that as soon as the pooled hypothesis has been rejected (e.g. H1), at least one of the two contained individual hypotheses (e.g. H4 and H5) must be false and there is only a potential for at most one type-I-error. Therefore H4 and H5 can be tested simultaneously once all higher-ranked hypotheses have been rejected. The same argument applies to H7 and H8 and to H9 and H10.

The following chart displays the testing strategy graphically:

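### The three SF-36 PCS objectives are worded as demonstrations of superiority but have no place in the 5% familywise procedure, and the pooled one has no specified contrast

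*Protocol*

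**What the plan says.** - **Objectives.** Protocol 2.2, objective 11, sets out to show at Week 12 that secukinumab proves "superior to placebo based on the change from baseline in health-related Quality of Life as measured by the SF-36 PCS". Objectives 12 and 13 repeat this for delayed and early tapering. SAP Table 1.2-1 carries all three and defines a pooled SF-36 endpoint.
- **Testing strategy.** Protocol 9.5.1 introduces its list of hypotheses by saying that "type-I-errors will be set such that a family-wise type-I-error of 5% is kept". The list in Protocol 9.5.1 and SAP 2.7.2 covers ASAS20, ASAS-NSAID and BASDAI only. It ends with H11, early tapering against placebo "with respect to change from baseline in total BASDAI score at Week 16".
- **Default level.** SAP 2.1 says that, unless otherwise stated, "the level of significance will be set to 5% (two-sided, family-wise type-I-error").
- **SF-36 analysis.** Both documents place SF-36 PCS after the testing strategy, among the other secondary variables. The model is an MMRM, with significance taken from pairwise comparisons of each regimen with placebo. No pooled contrast is named. The ASAS-NSAID paragraph does name one.
- **Power.** Protocol 9.7 states: "For SF-36 PCS, 62 patients per treatment group yield a power of approximately 87.5" per cent. The inputs behind that figure, a difference of 5.3 and an SD of 8.7, are given in the same sentence. SAP section 3 has no SF-36 power statement.

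**The concern.** The choice of verb in Protocol 2.2 looks deliberate. Objective 14 and the first five exploratory objectives speak of comparing or evaluating, while the primary objective and secondary objectives 1 to 13 speak of demonstrating superiority. Every objective in the second group has a hypothesis in the familywise procedure except the three on SF-36 PCS. A reader of the objectives, the power statement and the default 5% level could take an SF-36 result as confirmatory, but the testing strategy gives it no such standing. What is at stake is whether a quality-of-life claim can be made at all, and how three p-values will be described in the report. Separately, objective 11 cannot be tested from the SF-36 analysis paragraph, because that paragraph does not specify its contrast.

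**Working it through.** **1. Map objectives to hypotheses.**

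| Objective (Protocol 2.2 and 2.1) | Endpoint | Hypothesis |
|---|---|---|
| Primary | ASAS20 pooled, Week 12 | H1 |
| Secondary 1, 2 | ASAS-NSAID pooled; BASDAI pooled | H2, H3 |
| Secondary 3–5 | ASAS20 delayed W12; early W12; early W16 | H4–H6 |
| Secondary 6, 7 | ASAS-NSAID delayed; early | H7, H8 |
| Secondary 8–10 | BASDAI delayed W12; early W12; early W16 | H9–H11 |
| Secondary 11–13 | SF-36 PCS pooled; delayed; early | none |

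**2. Reproduce the stated SF-36 power.** Inputs from Protocol 9.7: difference 6.9 − 1.6 = 5.3, SD 8.7, 62 per group.

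SE = 8.7 × √(1/62 + 1/62) = 1.563, and 5.3/1.563 = 3.392.

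- Two-sided 5%: Φ(3.392 − 1.960) = 92.4%
- Two-sided 2.5%: Φ(3.392 − 2.241) = 87.5%, the stated figure

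So 87.5% reproduces at two-sided 2.5%, although the SF-36 sentence gives no level and 5% is the only one the plan states. The neighbouring BASDAI figure (about 91%) behaves the same way: 91.0% at 2.5% and 94.7% at 5%. Equal groups of 62 describe a single regimen against placebo, which is objectives 12 and 13. For the pooled objective, at about 190 patients:

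SE = 8.7 × √(1/63 + 1/127) = 1.341, and Φ(5.3/1.341 − 1.960) = 97.7%.

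For each regimen at 63 against 63, power is 92.8%. Both figures are at two-sided 5%.

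**3. False positives if all three tests were read as confirmatory.** With 1:1:1 allocation and no SF-36 effect, the two pairwise statistics correlate at 0.50 and each correlates at 0.87 with the pooled statistic. Simulating three equal-arm means (4 million draws) and counting any |z| > 1.96:

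| Tests counted | Either direction | Favouring secukinumab |
|---|---|---|
| Pooled, delayed, early | 9.7% | 4.8% |
| Delayed, early only (the contrasts actually written) | 9.1% | 4.5% |

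The three-test figure does not simply add to 5%, because the same patients and placebo arm are used. Under a global null, H1 plus the three SF-36 tests gives 11.9–14.2% in either direction, or 5.9–7.2% favouring secukinumab, for assumed between-endpoint correlations from 0.8 down to 0.

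**4. Effect of appending SF-36 after H11.** In a fixed sequence, a test placed last cannot change the level or power of those before it. Simulation with the plan's own passing rule (400,000 trials per scenario, 63 per arm) gave these familywise error rates:

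- global null: 5.0%
- SF-36 null in both arms, everything else strongly effective: 5.0%
- SF-36 null in the early arm only: 5.0–5.1%
- early arm null throughout: 5.0–5.1%

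**5. Chance of reaching SF-36.** All eleven hypotheses must be rejected in favour of secukinumab. Inputs from Protocol 9.7: ASAS20 56.9% against 27% or 35%; ASAS-NSAID difference 27.3, SD 40; BASDAI difference 1.8, SD 2.8. Assumed, because the documents give none: between-endpoint correlation 0 to 0.6, and Week 12 to Week 16 correlation 0.6 within an endpoint.

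| Placebo ASAS20 | All of H1–H11 rejected | Pooled SF-36 also rejected |
|---|---|---|
| 27% | 70–79% | 69–79% |
| 35% | 34–47% | 33–47% |

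At 35%, each single-regimen ASAS20 test has only about 70% power with 63 per arm. That is why the chain so often stops before H11.

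**The case against.** The plan does delimit its confirmatory family. The hypotheses form a closed list, the 5% claim is tied to that list, and SF-36 PCS appears afterwards under a separate heading. Other listed secondary variables also sit outside it, including BASDAI question 2 and the between-regimen ASAS-NSAID comparison. Leaving secondary endpoints outside familywise control is permissible. All of this stands, and it rules out a tempting reading: that the plan's 5% claim is broken. It is not, because that claim covers H1 to H11 only.

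Three other inferences also fail. A reader might add 9.7% to 5%, but the errors overlap. A reader might take 9.7% as the risk of a false claim of benefit, but only about half of it favours secukinumab. A reader might take all three objectives as powered, but the stated 87.5% concerns each regimen against placebo and not pooled objective 11.

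The objection does not explain why objectives 11 to 13 share the wording of the protected objectives. Nor does it supply the missing pooled contrast. No sentence labels the SF-36 tests as unprotected; their status has to be inferred from their absence from the list.

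**Conclusion.** The point holds as a mismatch between wording and procedure, plus one missing contrast. It is not an error in the testing strategy. As the plan stands, the chance of a confirmatory SF-36 conclusion is zero. Appending the tests would raise the chance for the pooled comparison to about 69–79% at 27% placebo response or 33–47% at 35%. Those ranges rest on the effect sizes in Protocol 9.7, 63 patients per arm with no dropout, and the assumed correlations. That the change leaves H1 to H11 untouched depends on none of these. The importance is modest: a cheap improvement that does not affect the primary conclusion.

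**What to change.** Before unblinding, in Protocol 9.5.1 and SAP 2.7.2:

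1. After H11, add H12: pooled secukinumab against placebo, SF-36 PCS change from baseline at Week 12.
2. Then add H13 (delayed) and H14 (early) as a simultaneous pair. The argument already used for H4 and H5 carries over: if the pooled effect is non-zero, at least one regimen differs from placebo.
3. Add to the SF-36 MMRM the linear contrast of the mean of the two regimens against placebo, as already written for ASAS-NSAID.
4. In Protocol 9.7, state the significance level behind the SF-36 and BASDAI power figures, or update them to 92.4% and 94.7% at two-sided 5%. Say that the SF-36 figure is per regimen.

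The cost is SAP wording, one contrast and a written protocol amendment with the approvals required by Protocol 11.1. No alpha or power is taken from H1 to H11. The limitation is that SF-36 becomes confirmatory only if all eleven earlier hypotheses are rejected.

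If the hierarchy is not extended, state in both documents that objectives 11 to 13 are not confirmatory and that their p-values are nominal. That also removes the mismatch, but item 3 is still needed for objective 11.
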